### 11.3.2. Total Safety cohort

Safety analysis based on all vaccination groups will include all subjects who were vaccinated per product information and have completed 30-day follow-up after at least one dose, regardless of the number of dose.

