4.1 Safety Analysis Set (Total Safety cohort)

In standard for re-examination of new drugs, etc.(2012), the point to reported is defined as follow. (Chapter II, no 3).

2) Patient Population for Surveillance

A) Patients planned to receive a drug under surveillance by investigator's medical judgment shall be defined as a subject.

- B) Subject who do not use within approved range shall not be included in the safety analysis set in principal.
- ※ However, if data of subject whose use is beyond approved range is collected, perform analysis as a separate item.
- C) How to actually select subjects shall be described in detail.

The definition of the safety analysis set to this study is as follows.

Subjects who have been completed 30-days follow-up after at least once vaccinated Cervarix, will be included in the safety analysis set.

The below cases shall be excluded from the safety analysis set in the following order.

- (1) Subject who consented prior to the site initiation date
- (2) Subject who completed administration of Cervarix prior to the site initiation date
- (3) Subject who completed administration of Cervarix prior to the consent date
- (4) Subject who did not receive Cervarix
- (5) Follow-up failure: Subject for whom adverse event status (Adverse events status is unknown or missing) could not be established
- (6) Subject who has been violated the inclusion/exclusion criteria

[Inclusion criteria]

- Subject or/and subjects whose parent(s)/Legally Acceptable Representative(s) [LAR(s)], in the opinion of the investigator, can and will comply with the requirements of the protocol (e.g., complete the diary cards, return for follow-up visits).
- Korean male or female subjects aged 9-25 years who are eligible for the series of Cervarix according to the locally approved PI.
- Written informed consent obtained from the subject/from the parent(s)/LAR of the subject.

[Exclusion criteria]

- At the time of PMS entry, the contraindications and precautions of use indicated in the locally approved PI. PI should be checked and the subject must not be included in the PMS if there is any contraindication.
- Subjects who had previous administration of a HPV vaccine other than Cervarix will not be enrolled into the study.
- Subjects who are not eligible for vaccination with Cervarix according to the medical judgement of physician

- Child in care.
- (7) Subject who has been violated the dosage
- [Dosage]
- Receive 0.5mL dose by intramuscular injection

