5.4 Methods for Missing Data and Incomplete Data

If there is missing or incomplete data, proceed as follows.

- If there is missing data that is not about this drug, it will be analyzed using intactly the data collected without replacement.
- Data including sign of inequality such as " ≥ 20 ", " > 20 " of continuous data used in analysis will be excluded from analysis.

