5.5 Other Statistical Considerations

The analysis will be performed considering the following, and if a separate consideration is required for each analysis item, the content will be described in section in 7.1 Derivation.

- All test statistics will be the results of two-sided test with the statistical significant level of 0.05.
- When calculating percentage in categorical variables in accordance with baseline background factor, the denominator will be defined by total number of subjects in each category. However, the denominator of detail items such as past / current medical history, Cervarix vaccination history, prior / concomitant medication, prior / concomitant vaccination will be defined by the number of subjects who recorded as 'Yes'.
- When calculating incidence proportion of adverse event in accordance with baseline background

factor, the denominator will be defined by the number of subjects in each category. However, the denominator of detail items such as past / current medical history, Cervarix vaccination history, prior / concomitant medication, prior / concomitant vaccination will be defined by the number of subjects in each category who recorded as 'Yes'.

- When calculating incidence proportion of adverse event such as adverse event, adverse drug reaction, serious adverse event, serious adverse drug reaction, unexpected adverse event, unexpected adverse drug reaction, unexpected serious adverse event, unexpected serious adverse drug reaction, unexpected non-serious adverse event and unexpected non-serious adverse drug reaction the denominator will be defined by the number of subjects in safety analysis set. Only in case of analysis by non-safety analysis set, the denominator is the number who does not include 'Subject who did not receive Cervarix' and 'Follow-up failure' of the total number of subjects excluded from safety analysis set.
- When calculating percentage in analysis of the variable collected only for some subjects such as pregnancy, the denominator will be defined by the number of subjects related with each variable.
- If the number of subjects with adverse event is less than 10, the analysis of incidence proportion of adverse event accordance with baseline background factor may be replaced with adverse event list.
- When more than 20% of expected frequency of the cell count is less than 5, Fisher's exact test should be used instead of Chi-square test.
- The 95% confidence interval will be estimated by using exact methods.

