6.8.1 Summary of Adverse Events

The summary table of adverse events will be presented about the following items. The number of

subjects, incidence proportion, its 95% confidence interval and the number of adverse events will be presented in the summary table. The analysis of adverse event/serious adverse event during the 30-day (Day 1 to Day 30) after each vaccine dose will be also performed separately.

- Adverse event (AE) · Adverse drug reaction (ADR) ^a
- Serious adverse event · Serious adverse drug reaction
- Unexpected adverse event ^b · Unexpected adverse drug reaction
- Unexpected serious adverse event · Unexpected serious adverse drug reaction
- Unexpected non-serious adverse event ^c · Unexpected non-serious adverse drug reaction

^a Adverse drug reaction (ADR): Adverse event that the 'relate to Cervarix' is 'Certain', 'Probable / Likely', 'Possible', 'Conditional / Unclassified' and 'Unassessable / Unclassifiable'

^b Unexpected adverse event: Adverse event that is not included in the local product insert

^c Unexpected non-serious adverse event: Adverse event that is non-serious and not included in the local product insert

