6.8.4 Adverse Events for Subjects in Non-Safety Analysis Set

According to chapter 2, Item 3 of the Ministry of Food & Drug Safety (MFDS) guideline, the incidence proportion of adverse event of subjects whose use is beyond approved range will be presented. However, 'subjects who have not taken this study drug' and 'follow-up failure' will be excluded from this analysis because their safety assessment is not available.

Below items of adverse event in accordance with SOC and PT or IT will be presented for the number of subjects, incidence proportion, its 95% confidence interval using exact method and the number of adverse events.

- Adverse event · Adverse drug reaction
- Serious adverse event · Serious adverse drug reaction
- Unexpected adverse event · Unexpected adverse drug reaction
- Unexpected serious adverse event · Unexpected serious adverse drug reaction
- Unexpected non-serious adverse event · Unexpected non-serious adverse drug reaction

Detailed adverse events will be listed by subjects for the following items

- Serious adverse event
- Unexpected adverse event
- Unexpected serious adverse event
- Adverse event of subject with liver disease
- Adverse event of subject with renal disease
- Adverse event leading to withdrawal

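### Follow-up failure is defined per subject while AE rates are planned per dose: if the stated denominator is used, a dose with unknown AE status dilutes its own rate

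*SAP*

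**What the plan says.** Entry to the safety set is decided per subject. SAP section 4.1 states: "Subjects who have been completed 30-days follow-up after at least once vaccinated Cervarix, will be included in the safety analysis set". Protocol section 11.3.2 likewise takes in subjects who "have completed 30-day follow-up after at least one dose, regardless of the number of dose". Exclusion (5) in SAP 4.1 is also written for the subject: "Follow-up failure: Subject for whom adverse event status (Adverse events status is unknown or missing) could not be established". SAP 6.8.4 says that follow-up failures "will be excluded from this analysis because their safety assessment is not available", which fits subjects with no usable window at all.

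The output is wanted per dose. SAP 6.8.1 says that the AE and SAE analysis "during the 30-day (Day 1 to Day 30) after each vaccine dose will be also performed separately". Protocol 11.5.2.1 asks for number, percentage and exact 95% CI for each dose, over all doses and by subject.

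On denominators, SAP 5.5 says that for AE incidence "the denominator will be defined by the number of subjects in safety analysis set". For variables collected in only some subjects, with pregnancy as the example, "the denominator will be defined by the number of subjects related with each variable". For baseline background factors it uses the subjects in each category, and SAP 7.2 lists order of vaccination among the categorised items. None of these rules names the by-dose tables of 6.8.1.

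On missing data, SAP 5.4 says that "it will be analyzed using intactly the data collected without replacement", but that sentence is limited to missing data that do not concern the study vaccine. Protocol 10.2.1 keeps all data up to a subject's withdrawal or last contact.

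**The concern.** A subject followed after dose 1 but never reached after dose 3 meets the entry rule and, on the natural reading of exclusion (5), stays in the safety set. The dose 3 window holds no information. Nothing in either document takes that single window out of the dose 3 rate. If the subject stays in the denominator, the effect is arithmetically the same as a window without an event.

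The loss is unlikely to be equal across doses. Under Table 3 of the protocol a diary card comes back at the next visit, by phone or by mail, and no visit follows Visit 3 (or Visit 2 on the two-dose schedule). The last dose therefore depends on phone or mail.

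The sole objective is the frequency and intensity of AEs, reported to the regulator. A rate that falls at the last dose for lack of data could be read as better tolerability with repeated dosing, and under-counting is the unsafe direction.

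**Working it through.** 1. The plan's own figures. Exact (Clopper-Pearson) limits at n = 600 reproduce all eight rows of Table 6 in Protocol 11.2, for example 10%: 7.7 to 12.7, and 20%: 16.9 to 23.4. The enrolment figure is 600 × 1.10 = 660. That 10% is a subject-level dropout allowance; since one completed window is enough to be evaluable, it does not give the share of dose windows with unknown status.

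2. Inputs that the documents do not give. The AE rate per dose (p), the share of recipients of dose k with unknown AE status (u), and the share of the safety set that receives dose k in the surveillance (r) are all assumed below. Unknown status is taken to be unrelated to AE risk.

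3. Unknown windows. With all recipients of dose k in the denominator, reported rate = p × (1 − u).
   - p = 20%: u = 5% gives 19.0%; u = 10% gives 18.0%; u = 15% gives 17.0%.
   - p = 10%: u = 10% gives 54/600 = 9.0% (exact 95% CI 6.8 to 11.6), against 54/540 = 10.0% (7.6 to 12.8) among windows with known status.

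4. Per-subject any-AE rate. Take three doses in the surveillance, independent windows, p = 20%, and 15% unknown after dose 3 only. True rate: 1 − 0.8 × 0.8 × 0.8 = 48.8%. Reported: 1 − 0.8 × 0.8 × (1 − 0.20 × 0.85) = 1 − 0.64 × 0.83 = 46.9%. The gap is 1.9 points.

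5. Non-recipients. Subjects on the two-dose schedule, or who entered after earlier doses, never receive some doses in the surveillance. With the whole safety set as denominator, reported rate = p × r × (1 − u). With p = 10%, r = 60%, u = 10% and a set of 600, there are 360 recipients, 324 with known status, and about 32 with an AE. The rate is 32/324 = 9.9% on known windows, 32/360 = 8.9% on recipients and 32/600 = 5.3% on the whole set. This can outweigh the effect of unknown status.

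6. A repair to avoid. Suppose incomplete windows are dropped unless an AE was reported in them. Per 100 recipients with p = 20% and 15 incomplete windows, there are 17 AEs in 85 known windows and 3 in the incomplete ones. If half of those 3 are reported, the rate is (17 + 1.5)/(85 + 1.5) = 18.5/86.5 = 21.4%. Inclusion then depends on the outcome, and the bias turns upward. Dividing the same 18.5 by all 100 recipients gives 18.5%, a lower bound.

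**The case against.** The strongest reply is that the dilution is inferred. No sentence records an unknown window as event-free, and SAP 5.4 does not do so: declining to replace missing data is not imputing no AE, and its condition may put vaccine safety data outside it. The by-dose denominator is not stated, and the mock tables are not available to settle it. All of this stands, so the point is conditional. It does not remove the gap, because the general rule in SAP 5.5 leads to the dilution. The other two denominators there, if stretched to doses, most naturally mean recipients, which leaves unknown windows in.

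Exclusion (5) could also be read as removing a subject with any unknown window, and then the dilution would not occur. The text does not rule this out, but it sits badly with entry after at least one followed dose and with the reason given in SAP 6.8.4. It would also discard valid windows.

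Mitigation is real. Protocol 6.4.10 requires at least three telephone attempts for unreturned cards, and details may be given by telephone. A subject who returns for dose 3 can hand in the dose 2 card then. Exposure is therefore mainly at the last dose of subjects with more than one dose in the surveillance; a subject whose only such dose is unknown is already removed by (5).

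Finally, 17.0% lies within Table 6's interval for an observed 20% (16.9 to 23.4). The shift may be modest beside sampling error, but it is systematic and the interval does not describe it.

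**Conclusion.** The point holds as a conditional one. Entry and exclusion work per subject, rates are planned per dose, and no rule covers a single dose with unknown AE status. With the safety set or all recipients as denominator, the by-dose rate falls by the factor (1 − u): from 20% to 19.0, 18.0 or 17.0% at u = 5, 10 or 15%. The whole-set denominator dilutes it further through non-recipients. The direction is down for any u above zero; the size cannot be taken from the documents.

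A reader might go further and infer that the plan scores missing windows as free of AEs, or that rates after later doses are certain to be biased down. The documents support neither. The first is a consequence of a denominator not expressly assigned to the by-dose tables. For the second, any dose with unknown status is affected, the last most, and the extent depends on follow-up that the plan actively pursues.

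The exact factor assumes that missing status is unrelated to AE risk; the any-AE figures also assume independent windows.

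**What to change.** - SAP 5.5 and 6.8.1: set the denominator for dose k to subjects who received dose k in the surveillance and have AE status established for Day 1 to 30. Print the number unknown beside it.
- List AEs reported in incomplete windows separately. As a sensitivity line, show the rate among all recipients of dose k counting every reported AE, labelled as a lower bound. Do not move into the main rate only those incomplete windows that have an AE.
- SAP 4.1: state that exclusion (5) removes a subject only when no dose in the surveillance has established AE status.
- Per-subject any-AE rate: add a sensitivity line restricted to subjects with known status after every dose received in the surveillance.

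The cost is a few sentences in the SAP and extra rows in the tables, with no new data collection. By-dose denominators become slightly smaller: at 20%, the exact interval goes from 16.9 to 23.4 with 600 subjects to 16.7 to 23.6 with 540. Known-status rates are themselves unbiased only if missingness is unrelated to AEs, which is why the count of unknowns and the sensitivity lines belong beside them.

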4.2 Non-Safety Analysis Set

The definition of the non-safety analysis set to this study is as follows.

Subjects who excluded from the safety analysis set except for 'Subject who did not receive Cervarix', 'Follow-up failure (unknown or missing adverse event status)'.

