### **8.3. Detecting and recording AEs, ADRs and SAEs (Amended: 14 May 2018)**

#### **8.3.1. Time period for detecting and recording AEs, ADRs and SAEs**

All AEs and SAEs starting immediately following administration of each dose of *Cervarix* must be recorded onto the CRF and all SAEs must be reported using the PMS SAE reporting form, the latter to be sent to GSK according to the required timelines, irrespective of intensity or whether or not they are considered vaccination-related.

The standard time period for collecting and recording SAEs will begin at the first receipt of *Cervarix* in the PMS and will end 30 days (**Day 1 to Day 30**) after the last dose of *Cervarix* administered during the subject's participation in PMS. See Section 8.4 for instructions on reporting and recording SAEs.

An overview of the protocol-required reporting periods for AEs, ADRs and SAEs is given in **Table 4**.

**CONFIDENTIAL**208710 (EPI-HPV-077 VS KR PMS)  
Protocol Amendment 1 Final**Table 4 Reporting periods for AEs, ADRs and SAEs**

PMS activity	V1	29 days post-V1		V2	29 days post-V2		V3	29 days post-V3
Reporting of AEs (expected & unexpected)								
Reporting of SAEs/ADRs and Pregnancy*								

V: vaccination; Post-V: post-vaccination

\* For subjects who become pregnant after receiving *Cervarix* during PMS, the pregnancy outcome (whether full-term or premature, information on the status of the mother and child) of these subjects will be followed-up for 6-8 weeks after delivery, if possible.

Note: Post-vaccination adverse events will be collected and reported only for *Cervarix* doses received within the PMS (after signing the ICF). Any adverse events collected after *Cervarix* doses received outside of this PMS shall be reported as a spontaneous report and shall follow guidance for reporting of spontaneous report.

All AEs reported within 30 days of each dose of the vaccine administered within the PMS and all SAEs reported throughout the PMS period up to 30 days (**Day 1 to Day 30**) after the last dose of *Cervarix* administered during the subject's participation in the PMS need to be recorded in the CRF. These AEs/ SAEs will be classified as expected/unexpected at the time of statistical analyses (refer to [GLOSSARY OF TERMS](#) for definitions of expected/unexpected adverse events).

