## 11.3. Study cohorts to be evaluated

### 11.3.1. Total Vaccinated cohort

The total vaccinated cohort will include all subjects who receive at least one dose of *Cervarix* in the PMS:

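### The adverse event incidence that SAP 6.8.4 presents as use outside the approved range is computed on a set that also admits subjects excluded only for administrative, consent or other non-label reasons

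*SAP*

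**What the plan says.** SAP 4.1 gives the regulatory basis for a separate analysis. Subjects treated outside the approved range are in principle kept out of the safety set, but "if data of subject whose use is beyond approved range is collected, perform analysis as a separate item".

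The same section lists seven exclusion reasons, applied in order:

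- (1) consent before site initiation;
- (2) vaccination completed before site initiation;
- (3) "Subject who completed administration of Cervarix prior to the consent date";
- (4) no Cervarix received;
- (5) follow-up failure, meaning unknown or missing AE status;
- (6) breach of an inclusion or exclusion criterion;
- (7) breach of the listed dosage.

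SAP 4.2 defines the non-safety set as "Subjects who excluded from the safety analysis set except for 'Subject who did not receive Cervarix", with reason (5) left out in the same way. SAP 5.5 matches this in its rule for percentages: "the denominator is the number who does not include 'Subject who did not receive Cervarix' and 'Follow-up failure' of the total number of subjects", counted among those left out of the safety set.

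SAP 6.8.4 then states what the analysis is for: "the incidence proportion of adverse event of subjects whose use is beyond approved range will be presented". It leaves out the unvaccinated and the follow-up failures because their safety cannot be assessed.

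Two protocol passages bear on who can contribute AEs. Section 8.3.1 (note to Table 4) says "Post-vaccination adverse events will be collected and reported only for" doses given within the surveillance after the consent form is signed; AEs after other doses go to spontaneous reporting. Section 11.3.1 says "The total vaccinated cohort will include all subjects who receive at least one dose of" the vaccine, with the qualifier that the dose is given within the surveillance. SAP 4 bases all its sets on the Total Vaccinated cohort but describes it without that last qualifier.

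**The concern.** The set definition and the stated purpose do not match. The guideline item asks about use outside the label. The set answers a different question: what happened to everyone left out of the safety set whose AE status was thought to be available. A 16-year-old vaccinated exactly to the label, who signed consent before the site was formally initiated, would count as use outside the approved range.

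This table is the SAP's response to a specific guideline item, and the analyses are reported to the MFDS. If on-label vaccinees, or subjects with no dose under observation, are mixed in, the figure no longer describes off-label safety. An informal comparison with the safety-set incidence could then mislead.

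**Working it through.** **Step 1. Which reasons reach the set.** Seven reasons less (4) and (5) leave (1), (2), (3), (6) and (7).

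| Reason | Subject matter | Label criterion? |
|---|---|---|
| (1) | Consent date against site initiation | No |
| (2) | Completion of vaccination against site initiation | No |
| (3) | Completion of vaccination against consent date | No |
| (6) | Mixed list of entry criteria | Age, PI eligibility and PI contraindication: yes. Written consent, child in care, expected compliance: not on their face |
| (7) | Volume, route, schedule | Yes |

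Three of the five are administrative, one is mixed and one is squarely about the label.

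**Step 2. Can subjects under (2) and (3) contribute AEs?** A subject under (3) finished vaccination before consent, so has no dose given after the consent form was signed. Suppose each subject is assigned the first reason that applies. Then a subject under (2) has already passed (1), so:

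vaccination completed < site initiation ≤ consent date.

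That subject has no post-consent dose either. Under protocol 8.3.1 no AEs are collected for such doses. If these subjects remain in the set, they add to the denominator without a surveillance-collected numerator. Whether they remain depends on the base cohort. Under the protocol's definition (a dose in the PMS) they would drop out before SAP 4.2 applies. Under the SAP's shorter description they stay in. The SAP also lists (2) and (3) as exclusions without removing them in 4.2. The texts do not settle the matter.

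This does not extend to reason (1). Someone who consented early may have been dosed and fully followed afterwards.

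**Step 3. Effect of the order.** On the same first-match reading, a subject who meets any of (1) to (3) and also has unknown AE status is classed before (5) is reached. That subject stays in the denominator, against the reason SAP 6.8.4 gives for removing follow-up failures. Conversely, a subject with a real dosage breach who also meets (1) is never labelled (7).

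**Step 4. Is the mixture separated anywhere?** SAP 6.1 tabulates the reasons as disposition counts. No planned AE table is split by reason. The opening of SAP 6.8 also runs the 6.8.1 summary on the non-safety set, although the footnote to the table at the start of SAP 6 limits that set to 6.8.4.

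**Step 5. Size.** The documents give no expected size, mix or AE rate for this set, so there is no plan figure to reproduce. The illustration below is entirely assumed: 60 subjects in the set and 30% true AE incidence in off-label use. Let f be the share of non-label subjects and p their recorded AE incidence:

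reported incidence = 0.30 × (1 − f) + p × f

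| f | p = 10% | p = 0 |
|---|---|---|
| 0 | 30.0% | 30.0% |
| 25% | 25.0% | 22.5% |
| 50% | 20.0% | 15.0% |
| 75% | 15.0% | 7.5% |
| 90% | 12.0% | 3.0% |

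The p = 0 column is the extreme case and could apply only to (2) and (3). If p equals 30%, nothing moves. If p exceeds 30%, the figure rises: at p = 40% and f = 50% it is 0.15 + 0.20 = 35%.

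Intervals at f = 50%, by the exact method that SAP 5.5 specifies:

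- Off-label subjects only: 30 × 0.30 = 9 events, 9/30 = 30% (95% CI 14.7 to 49.4).
- Pooled, p = 10%: 9 + 30 × 0.10 = 12 events, 12/60 = 20% (10.8 to 32.3).
- Pooled, p = 0: 9/60 = 15% (7.1 to 26.6).

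**The case against.** The strongest reply is that this is a labelling slip in one secondary descriptive table. SAP 6.1 will show the reasons, so a reader can see what the set is made of. SAP 6.8.4 adds by-subject listings of serious and unexpected AEs, and its heading names the non-safety set rather than off-label use. No test against the safety set is planned, and the mock tables are not shown, so the final label is unknown. The limited impact stands. The rest does not cure the mismatch: disposition counts do not let a reader recover AE incidence by reason, and the text of 6.8.4 still states what the figure is meant to be.

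A reader might also infer more than the documents support:

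- *That most of the set is administrative.* No counts by reason are given; the share could be zero.
- *That none of the retained reasons other than dosage concerns the label.* Reason (6) includes age, PI eligibility and PI contraindications.
- *That zero-AE subjects certainly dilute the rate.* This is confined to (2) and (3), and only if the base cohort keeps them. For (1) and the non-label parts of (6), AEs may be fully collected and the direction of any shift is open.
- *That the table broadly uses data without consent.* Subjects under (1) and (3) did consent, and the consent form covers collection and handling of safety information rather than vaccination (protocol 3 and 6.4.2). Only the missing-written-consent part of (6) raises that question.

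**Conclusion.** The point holds as a mismatch between an analysis set and the quantity it is said to estimate. It can be read from the SAP alone and does not depend on the illustration: a single on-label subject excluded under (1) to (3) makes the description in 6.8.4 wrong, and the SAP provides for such subjects by listing those reasons. The numerical effect is unknown. On the assumed values it runs from none to a true 30% shown as 3% in the extreme case, and it could go upward.

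The ordering results rest on first-match assignment, which is the natural reading of the SAP's instruction but is not spelled out. The effect is confined to the AE outputs for the non-safety set: 6.8.4 and, if run, the 6.8.1 summary. The main safety-set incidence is untouched. It should be corrected because the figure answers a regulatory item and the correction is cheap.

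**What to change.** 1. In SAP 6.8.4, and in the matching denominator in 5.5, replace the catch-all set with a direct flag for use outside the approved range. Apply it to every subject with at least one surveillance dose and known AE status. Base it on the label-related criteria: dosage as listed in (7), and age, PI eligibility and PI contraindication within (6). Set it **regardless of which exclusion reason comes first**. Building the set from the assigned reason alone would lose off-label subjects already classed under (1).
2. Remove subjects with unknown AE status wherever they fall in the order.
3. State for each remaining criterion in (6) whether it is a label criterion. Previous use of another HPV vaccine and the physician's judgement of ineligibility are not settled by the SAP text.
4. Show subjects excluded only for administrative, consent or other non-label reasons in the 6.1 disposition table, with any known AEs in a separate by-subject listing.
5. Reconcile SAP 4 with protocol 11.3.1 on whether the Total Vaccinated cohort requires a dose in the PMS. Align the SAP 6 footnote with the opening of 6.8 on whether 6.8.1 is run for this set.

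The cost is wording in SAP 4, 4.2, 5.5, 6 and 6.8.4 and one extra listing. The calculation in Step 5 shows the price in precision: fewer subjects and a wider interval, but around the quantity the section says it reports.
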